**Appendix 2**  
**Schedule of Activities: Optional Active Treatment Extension**

## Appendix 2: Schedule of Activities for Optional Active Treatment Extension

---

ADA=anti-drug antibody; ATE=active treatment extension; CRP=C-reactive protein; FeCal=fecal calprotectin; NA=not applicable; PK=pharmacokinetic; PRO=patient-reported outcome; [REDACTED] SC=study completion; TD=treatment discontinuation; UC-PRO/SS=Ulcerative Colitis Patient-Reported Outcomes Signs and Symptoms; UV=unscheduled visit.

**Notes: On treatment days, all assessments should be performed prior to study treatment administration, unless otherwise specified.**

**Patients must complete induction treatment and assessments through [REDACTED] to continue into active treatment extension.**

*Assessments shaded in gray are not applicable for sites in China.*

- a Patients who complete the active treatment extension period will return to the clinic for a study completion visit at [REDACTED]
- b Patients who discontinue study treatment prematurely will return to the clinic for a treatment discontinuation visit within 14 days after their final dose of study treatment and will then enter the safety follow-up period.
- c Patients who complete the active treatment extension period and patients who discontinue study treatment prior to [REDACTED] will undergo follow-up assessments at [REDACTED] after their final dose of study treatment.
- d Unscheduled visits may be performed if clinically indicated (e.g., for evaluation of an adverse event). The specified assessments are required at each unscheduled visit, unless otherwise specified. Assessments listed in parentheses are not required, but may be performed for patients who receive rescue therapy or experience persistent or worsening disease for which rescue therapy is indicated, as determined by the investigator. Additional assessments may be performed if clinically indicated, as determined by the investigator.
- e Samples will be analyzed for culture and sensitivity, ova and parasites, and *C. difficile*.
- f Stool samples should be obtained prior to bowel preparation for endoscopy (colonoscopy or sigmoidoscopy), if applicable.

## Appendix 2: Schedule of Activities for Optional Active Treatment Extension

---

- g Patients assigned to the vixarelimab [REDACTED] arm or to the placebo arm during induction will receive [REDACTED] vixarelimab [REDACTED] during ATE. Patients assigned to the vixarelimab [REDACTED] arm will continue to receive [REDACTED] vixarelimab Q4W during ATE. To maintain blind, patients assigned to receive vixarelimab [REDACTED] during ATE will also receive placebo [REDACTED] (see Section 3.1.1).
- h After informed consent has been obtained but prior to initiation of study treatment, only serious adverse events caused by a protocol-mandated intervention should be reported. After initiation of study treatment, all adverse events will be reported until [REDACTED] the final dose of study treatment. After this period, the Sponsor should be notified if the investigator becomes aware of any serious adverse event that is believed to be related to prior exposure to study treatment (see Section 5.6).
- i Includes evaluation of the head, eyes, ears, nose, and throat, and the cardiovascular, dermatologic, musculoskeletal, respiratory, gastrointestinal, genitourinary, and neurologic systems.
- j Perform a limited, symptom-directed examination at specified timepoints or as clinically indicated.
- k ECG recordings should be performed prior to *invasive* procedures scheduled at that same time (e.g., blood draws). *Vital sign measurements, physical examinations, and diary training may be conducted prior to performing the ECG. See Section 4.5.5.*
- l Urine pregnancy tests will be reviewed prior to each study drug administration for confirmation of a negative result. If a urine pregnancy test is positive, it must be confirmed by a serum pregnancy test.
- m Video recordings should be taken of the entire endoscopic procedure, starting from insertion into the bowel. Biopsies should be performed upon withdrawal of the endoscope from the bowel. Technical instructions for video recording and biopsy collection will be provided in the endoscopy and/or laboratory manual.
- n Tissue collected will be used for histologic assessments and exploratory biomarker research *at participating sites, excluding China (see Appendix 9). For endoscopy assessments after screening for sites located in China, endoscopy will be performed but no biopsy will be collected.*
- o See Appendix 3. *The Mayo Score will be calculated by the Sponsor.*
- p Clinician-reported outcome instruments will be completed after the physical examination, prior to the administration of study treatment.
- q An electronic diary will be used to collect PRO data, including stool frequency/rectal bleeding and the UC-PRO/SS instrument (see Section 4.5.7.2). Stool frequency, rectal bleeding, and UC-PRO/SS will be collected daily over at least a 7-day period before each specified study visit.
- r On treatment days, all samples should be collected prior to dosing.
- s Additional ADA samples should be collected in patients with signs and symptoms of injection-related reactions.

## Appendix 3 Mayo Score

The Mayo Score is a composite endpoint consisting of patient-reported outcomes (stool frequency, rectal bleeding), endoscopy, and clinician-reported outcome (Physician's Global Assessment) components. Each component is scored on a scale from 0 to 3, and totaled for a maximum score of 12.

The modified Mayo Score (mMS) is a composite of stool frequency, rectal bleeding, and centrally read endoscopy. Maximum total score of 9.

**1. Stool frequencya**

- 0 = Normal number of stools for this patient
- 1 = 1–2 more stools than normal
- 2 = 3–4 more stools than normal
- 3 = 5 or more stools than normal

**2. Rectal bleedingb**

- 0 = No blood seen or no bowel movement
- 1 = Stool with streaks of blood
- 2 = Stool with more than streaks of blood
- 3 = Blood alone passed

**3. Endoscopy**

- 0 = Normal appearance of mucosa
- 1 = Mild disease (erythema, decreased vascular pattern), no friability
- 2 = Moderate disease (marked erythema, absent vascular pattern, friability, erosions)
- 3 = Severe disease (spontaneous bleeding, ulceration)

**4. Physician's Global Assessment**

- 0 = Normal
- 1 = Mild
- 2 = Moderate
- 3 = Severe

a Each patient provides own baseline against which to compare the degree of abnormality in stool frequency.

b Represents the worst bleeding score for that day.

**Appendix 4**  
**Ulcerative Colitis Patient-Reported Outcome Signs and Symptoms (UC-PRO/SS)**

**You and Your Ulcerative Colitis**

The following questions ask about your bowel movements in the **past 24 hours**.

For these questions, a ***bowel movement*** is defined as any time you pass solid or liquid including stool, blood, mucus (white material), or water. Passing gas alone is not considered a bowel movement.

1. In the past 24 hours, how many bowel movements did you have? Please select one response.
	
 0  1-2  3-4  5-6  7-9  10-12  13-17  18 or more

2. In the past 24 hours, how often were your bowel movements mostly or completely liquid? Please select one response.
	
 Never  Rarely  Sometimes  Often  Always

#### Appendix 4: Ulcerative Colitis Patient-Reported Outcome Signs and Symptoms (UC-PRO/SS)

The following questions ask about the presence and how often you experienced your ulcerative colitis symptoms in the **past 24 hours**.

Please answer each question by selecting yes or no.		If Yes, how often did you experience this symptom? Please select one response.
3. In the past 24 hours, did you have blood in your bowel movements?	 Yes  No	1  Rarely    2  Sometimes    3  Often    4  Always
4. In the past 24 hours, did you have mucus (white material) in your bowel movements?	 Yes  No	1  Rarely    2  Sometimes    3  Often    4  Always
5. In the past 24 hours, did you have stool, blood, or liquid leak out before you reached a toilet?	 Yes  No	1  Rarely    2  Sometimes    3  Often    4  Always
6. In the past 24 hours, did you pass gas?	 Yes  No	1  Rarely    2  Sometimes    3  Often    4  Very Often

The following questions ask about the presence and severity of your ulcerative colitis symptoms in the **past 24 hours**.

Please answer each question by selecting yes or no.		If Yes, how severe was this symptom at its worst? Please select one response.
7. In the past 24 hours, did you feel the need to have a bowel movement right away?	 Yes  No	1  Mild    2  Moderate    3  Severe    4  Very Severe
8. In the past 24 hours, did you feel pain in your belly?	 Yes  No	1  Mild    2  Moderate    3  Severe    4  Very Severe
9. In the past 24 hours, did you feel bloating in your belly?	 Yes  No	1  Mild    2  Moderate    3  Severe    4  Very Severe

## **Appendix 5**

### **Anaphylaxis Precautions**

These guidelines are intended as a reference and should not supersede pertinent local or institutional standard operating procedures.

#### **REQUIRED EQUIPMENT AND MEDICATION**

The following equipment and medication are needed in the event of a suspected anaphylactic reaction during study treatment administration in a clinical setting:

- Monitoring devices: ECG monitor, blood pressure monitor, oxygen saturation monitor, and thermometer
- Oxygen
- Epinephrine for intramuscular (preferred route), SC, IV, or endotracheal administration in accordance with institutional guidelines
- Antihistamines
- Corticosteroids
- IV infusion solutions, tubing, catheters, and tape

#### **PROCEDURES**

In the event of a suspected anaphylactic reaction during study treatment administration, the following procedures should be performed:

- Stop the study treatment administration, if possible.
- Call for additional medical assistance.
- Maintain an adequate airway.
- Ensure that appropriate monitoring is in place, with continuous ECG and pulse oximetry monitoring if possible.
- Administer antihistamines, epinephrine, or other medications and IV fluids as required by patient status and as directed by the physician in charge.
- Continue to observe the patient and document observations.
- Collect serum samples for immunogenicity testing.
- Ask the patient to return for immunogenicity sample collection at the time of washout, if appropriate.

## Appendix 6

### Investigational and Non-Investigational Medicinal Product Designations (for Use in European Economic Area and United Kingdom)

**Table 1 Investigational, Authorized Auxiliary, and Unauthorized Auxiliary Medicinal Product Designations for European Economic Area**

Product Name	IMP/AxMP Designation	Marketing Authorization Status in EEA	Used within Marketing Authorization
Vixarelimab (RO7622888)	IMP (test product)	Not approved	Not applicable
Vixarelimab placebo	IMP (placebo)	Not approved	Not applicable
Topical 5-ASA	AxMP (rescue therapy)	Approved	Yes
Oral 5-ASA	AxMP (other a )	Approved	Yes
IV corticosteroids and rectal corticosteroids (i.e., enemas or suppositories)	AxMP (rescue therapy)	Approved	Yes
Oral corticosteroids	AxMP (other a )	Approved	Yes
AZA	AxMP (other a )	Approved	Yes
6-MP	AxMP (other a )	Approved	Yes
MTX	AxMP (other a )	Approved	Yes

5-ASA=5-aminosalicylic acid; 6-MP=6-mercaptopurine; AxMP=auxiliary medicinal product; AZA=azathioprine; EEA=European Economic Area; IMP=investigational medicinal product; MTX=methotrexate.

a Used as a background or rescue therapy; will differ patient to patient.

**Appendix 6: Investigational Medicinal Product and Non-Investigational Medicinal Product Designations (for Use in European Economic Area and United Kingdom)**

**Table 2 Investigational and Non-Investigational Medicinal Product Designations for United Kingdom**

Product Name	IMP/NIMP Designation	Marketing Authorization Status in U.K.	Used within Marketing Authorization
Vixarelimab (RO7622888)	IMP (test product)	Not Approved	Not applicable
Vixarelimab placebo	IMP (placebo)	Not Approved	Not applicable
Topical 5-ASA	NIMP (rescue therapy)	Approved	Yes
Oral 5-ASA	NIMP (other a )	Approved	Yes
IV corticosteroids and rectal corticosteroids (i.e. enemas or suppositories)	NIMP (rescue therapy)	Approved	Yes
Oral corticosteroids	NIMP (other a )	Approved	Yes
AZA	NIMP (other a )	Approved	Yes
6-MP	NIMP (other a )	Approved	Yes
MTX	NIMP (other a )	Approved	Yes

5-ASA=5-aminosalicylic acid; 6-MP=6-mercaptopurine; AZA=azathioprine; EEA=European Economic Area; IMP=investigational medicinal product; MTX=methotrexate; NIMP=non-investigational medicinal product.

a Used as a background or rescue therapy; will differ patient to patient.

## Appendix 7

### Division of AIDS (DAIDS) Table for Grading the Severity of Adult and Pediatric Adverse Events

The investigator will use the Division of AIDS (DAIDS) Table for Grading the Severity of Adult and Pediatric Adverse Events (HHS 2017), with slight modifications for clarity and for alignment with internal practices, for assessing the severity of each adverse event reported during the study.

**Table 1 Severity Grading for Adult and Pediatric Adverse Events**

Parameter	Grade 1 (Mild)	Grade 2 (Moderate)	Grade 3 (Severe)	Grade 4 (Potentially Life-Threatening)
Cardiovascular				
Arrhythmia (by ECG or physical examination) (Specify type if applicable)	No symptoms and no intervention indicated	No symptoms and non-urgent intervention indicated	Non-life-threatening symptoms and non-urgent intervention indicated	Life-threatening arrhythmia or urgent intervention indicated
Hypertension (with the lowest reading taken after repeat testing during a visit): ≥ 18 years of age	140 to < 160 mmHg systolic or 90 to < 100 mmHg diastolic a	≥ 160 to < 180 mmHg systolic or ≥ 100 to < 110 mmHg diastolic a	≥ 180 mmHg systolic or ≥ 110 mmHg diastolic a	Life-threatening consequences in a participant not previously diagnosed with hypertension (e.g., malignant hypertension) or hospitalization indicated
Hypertension (with the lowest reading taken after repeat testing during a visit): < 18 years of age b	> 120 mmHg systolic or > 80 mmHg diastolic, but systolic and diastolic < 95th percentile adjusted for age, height, and sex	≥ 95th to < 5 mmHg above the 99th percentile adjusted for age, height, and sex (systolic and/or diastolic) a	≥ 5 mmHg above the 99th percentile adjusted for age, height, and sex (systolic and/or diastolic) a	Life-threatening consequences in a participant not previously diagnosed with hypertension (e.g., malignant hypertension) or hospitalization indicated
Hypotension	No symptoms	Symptoms corrected with oral fluid replacement	Symptoms and IV fluids indicated	Shock requiring use of vasopressors or mechanical assistance to maintain blood pressure

a When systolic and diastolic blood pressures meet criteria for different grades, the higher grade should be used.

b Blood pressure norms for children < 18 years of age can be found in: Expert Panel on Integrated Guidelines for Cardiovascular Health and Risk Reduction in Children and Adolescents; National Heart, Lung, and Blood Institute. Expert panel on integrated guidelines for cardiovascular health and risk reduction in children and adolescents: summary report. Pediatrics 2011;128(Suppl 5):S213–56.

**Appendix 7: Division of AIDS (DAIDS) Table for Grading the Severity of Adult and Pediatric Adverse Events**

**Table 1 Severity Grading for Adult and Pediatric Adverse Events (cont.)**

Parameter	Grade 1 (Mild)	Grade 2 (Moderate)	Grade 3 (Severe)	Grade 4 (Potentially Life-Threatening)
Cardiovascular (cont.)				
Cardiac ischemia or infarction (Report the most appropriate term)	—	—	New symptoms with ischemia (stable angina) or new testing consistent with ischemia	Unstable angina or acute myocardial infarction
Heart failure	No symptoms and laboratory or cardiac imaging abnormalities	Symptoms with mild to moderate activity or exertion	Symptoms at rest or with minimal activity or exertion (e.g., hypoxemia) or intervention indicated (e.g., oxygen)	Life-threatening consequences or urgent intervention indicated (e.g., vasoactive medications, ventricular assist device, heart transplant)
Hemorrhage (with significant acute blood loss)	—	Symptoms and no transfusion indicated	Symptoms and transfusion of ≤2 units packed RBCs (for children, packed RBCs ≤10 cc/kg) indicated	Life-threatening hypotension or transfusion of >2 units packed RBCs (for children, packed RBCs >10 cc/kg) indicated
Prolonged PR interval or AV block: >16 years of age (Report the most appropriate term)	PR interval 0.21 to <0.25 seconds	PR interval ≥0.25 seconds or Type I second-degree AV block	Type II second-degree AV block or ventricular pause ≥3.0 seconds	Complete AV block
Prolonged PR interval or AV block: ≤16 years of age (Report the most appropriate term)	First-degree AV block (PR interval >normal for age and rate)	Type I second-degree AV block	Type II second-degree AV block or ventricular pause ≥3.0 seconds	Complete AV block
Prolonged QTc interval (corrected per Bazett's formula)	0.45 to 0.47 seconds	>0.47 to 0.50 seconds	>0.50 seconds or ≥0.06 seconds above baseline	Life-threatening consequences (e.g., torsade de pointes, other associated serious ventricular dysrhythmia)

AV = atrioventricular.

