Occasional use of NSAIDs [e.g., headache, arthritis, myalgias, or menstrual cramps] and aspirin (up to 325 mg/day) is permitted.

- Participation in an investigational study involving non-biologic therapy within *4 weeks* or 5 half-lives of the investigational product (whichever is greater) prior to screening, or biologic therapy (including vaccines) within 8 weeks or 5 half-lives of the investigational product (whichever is greater) prior to screening
- Treatment with any live-attenuated vaccine within 4 weeks prior to screening or intended to receive such during the study.

Uses of non-live (inactivated) vaccines are allowed.

- Treatment with immunoglobulin or blood products within 4 weeks prior to screening, or any condition that is likely to require such treatment during the course of the study, unless the treatment is deemed acceptable by the investigator, in consultation with the Medical Monitor
- Conditions other than UC that could require treatment with > 20 mg/day of prednisone (or equivalent) during the course of the study, *per the investigator's assessment*
- Significant uncontrolled medical condition or comorbidity, such as cardiac (e.g., moderate to severe heart failure New York Heart Association Class III/IV or historical evidence of left ventricular ejection fraction <35%), pulmonary, renal, hepatic, endocrine, or gastrointestinal disorders (excluding UC) that in the opinion of the investigator, would confound the study results or compromise patient safety
- Hospitalized (other than for elective reasons) during the screening period
- History of malignancy within the 5 years prior to screening, with the exception of basal cell or squamous cell skin neoplasms

In addition, a malignant diagnosis or condition that occurred more than 5 years prior to screening, and any basal cell or squamous cell neoplasm must be considered cured, inactive, and not under treatment.

- History or presence of complete left bundle branch block, second- or third-degree atrioventricular heart block, *or other abnormal ECG finding during screening that is deemed clinically significant by the investigator*
- QT interval corrected through use of Fridericia's formula (QTcF) >450 ms if patient is male or QTcF >470 if patient is female

For male or female patients with QRS > 120: QTcF >480 ms

- Acquired or congenital immunodeficiency
- Positive HIV antibody test at screening

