#### **4.5.5      Electrocardiograms**

Single 12-lead ECG recordings will be obtained at specified timepoints (see [Appendix 1](#) and [Appendix 2](#)) and may be obtained at unscheduled timepoints as indicated.

All ECG recordings must be performed on a device that is equipped with reliable, automated algorithms for measuring heart rate and ECG intervals and capable of local printing. Paper copies of ECG tracings will be kept as part of the patient's permanent study file at the site.

Lead placement should be as consistent as possible. ECG recordings should be performed after the patient has been resting in a supine or semi-supine position for at least 10 minutes, and the patient should remain in a supine or semi-supine position during recording. The same positioning should be maintained for each patient throughout the study. ECG recordings should be performed prior to *invasive* procedures scheduled at that same time (e.g., blood draws) and should not be performed within

2.5 hours after any meal. *Vital sign measurements, physical examinations, and diary training may be conducted prior to performing the ECG.* Circumstances that may induce changes in heart rate, including environmental distractions (e.g., television, radio, conversation), should be avoided during the pre-ECG resting period and during ECG recording.

Paper copies of all ECG tracings must be reviewed, annotated to indicate any clinical findings, signed, and dated by a medically qualified member of the site staff. For each timepoint, heart rate, RR interval, PR interval, QRS interval, uncorrected QT interval, and QTcF based on machine readings of ECG tracings should be recorded on the appropriate eCRF. Any morphologic waveform changes or other ECG abnormalities must be documented on the eCRF.

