If at a particular postdose timepoint the mean QTcF is >500 ms or >60 ms longer than the baseline value (i.e., last value prior to initiation of study treatment), another ECG must be recorded, ideally within the next 5 minutes, and ECGs should be repeated at least hourly until two successive ECGs show resolution of the findings. A PK sample should be obtained if not already scheduled for that timepoint. The Medical Monitor should be notified, and standard-of-care treatment may be instituted at the discretion of the investigator. A decision on study treatment discontinuation should be made, as described in Section 5.1.2.2. The investigator should also evaluate the patient for potential concurrent risk factors (e.g., electrolyte abnormalities, concomitant medications known to prolong the QT interval, severe bradycardia).

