## **6.5      SAFETY ANALYSES**

The safety analysis population will consist of all randomized patients who received at least one dose of study treatment, with patients grouped according to treatment received.

Safety will be assessed by adverse events, clinical laboratory evaluations, vital signs, and ECGs.

Separate summaries of adverse events will be provided for the screening period, the induction period, and optional ATE period. Adverse events will be summarized by treatment arms.

All verbatim adverse event terms will be mapped to Medical Dictionary for Regulatory Activities thesaurus terms, and adverse event severity will be graded according to DAIDS toxicity grading scale.

Relevant laboratory, vital sign (e.g., pulse rate), and ECG data will be displayed by time, with grades identified where appropriate.

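### Appendix 7 grades QTc prolongation by Bazett while the trial screens, records and monitors QTcF, so near a cut-point heart rate alone can create or hide a QTc grade

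*Combined protocol and SAP*

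**What the plan says.** Three operative rules use Fridericia:

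- **Eligibility (Section 4.1.2).** The limits are on QTcF: above 450 ms excludes men, "QTcF >470 if patient is female" (in ms) excludes women, and above 480 ms excludes either sex when QRS exceeds 120.
- **Data capture (Section 4.5.5).** Sites enter heart rate, RR, PR and QRS, together with "uncorrected QT interval, and QTcF based on machine readings of ECG tracings should be recorded on the appropriate eCRF". Bazett's value (QTcB) is not requested.
- **Post-dose trigger (Section 4.5.5).** The rule begins "If at a particular postdose timepoint the mean QTcF is" and fires above 500 ms or at more than 60 ms over baseline.

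The grading table uses Bazett. In Appendix 7, Table 1 (Cardiovascular), the row is "Prolonged QTc interval (corrected per Bazett's formula". Grade 1 is "0.45 to 0.47 seconds" and Grade 2 is ">0.47 to 0.50 seconds". Grade 3 is above 0.50 seconds or "≥0.06 seconds above baseline". Grade 4 is defined by life-threatening consequences.

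The table is operative. Section 5.3.3 requires investigators to use it, with slight modifications that the protocol allows itself, for every adverse event, and adverse event severity is a secondary safety endpoint (Section 2, Table 1). Section 6.5 adds that "ECG data will be displayed by time, with grades identified where appropriate". Nothing in the protocol says to derive QTcB for grading or to apply the Appendix 7 bands to QTcF.

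**The concern.** A grade should be assigned to the quantity that is measured and acted on. Here the trial screens, records and monitors one QTc and grades another. The ratio of the two depends only on heart rate, so a patient whose QTcF does not move can gain or lose a grade because the pulse moved, and a patient who meets the QTcF trigger can receive a low grade.

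Grades may also differ between sites. An investigator has a machine-read QTcF to hand and a table labelled Bazett. One site may apply the bands to QTcF and another may calculate QTcB, so that identical tracings are graded differently. What is at stake is how well QTc grades can be interpreted in the ECG displays and in any QTc adverse event.

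**Working it through.** The plan states no figure on this point, so there is none to reproduce. The check applies the definitions of the two corrections.

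**Inputs.** The grade bands come from Appendix 7, and the QTcF limits and trigger from Sections 4.1.2 and 4.5.5. Heart rate (HR) is an assumption, shown from 50 to 100 bpm, because the documents give no heart-rate or QTc distribution.

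**Formula.** With RR = 60/HR in seconds, QTcB = QT/RR^(1/2) and QTcF = QT/RR^(1/3). Hence QTcB = QTcF × RR^(−1/6) = QTcF × (HR/60)^(1/6).

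| HR (bpm) | QTcB/QTcF | QTcB when QTcF = 430 ms | Grade on QTcB |
|---|---|---|---|
| 50 | 0.970 | 417 | none |
| 60 | 1.000 | 430 | none |
| 80 | 1.049 | 451 | 1 |
| 100 | 1.089 | 468 | 1 |

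On QTcF, 430 ms is ungraded in every row. The table and the next two bullets use the absolute bands, so they assume a rise from baseline of less than 60 ms.

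- **Grade created.** The 80 and 100 bpm rows above.
- **Grade hidden.** QTcF 460 ms at 50 bpm gives 460 × 0.970 = 446 ms. That is Grade 1 on QTcF and ungraded on QTcB.
- **Change criterion missed.** QTcF rises from 400 to 465 ms (+65 ms, so the trigger fires) while heart rate falls from 80 to 60 bpm. QTcB goes from 400 × 1.049 = 420 ms to 465 × 1.000 = 465 ms, which is +45 ms. The table gives Grade 1 on the absolute band; the same bands on QTcF give Grade 3, because 65 ms is at least 60 ms.
- **High value at a slow rate.** QTcF 505 ms at 50 bpm gives 505 × 0.970 = 490 ms. This is Grade 2 only if baseline QTcB was above 430 ms (490 − 60). At or below that baseline, the change criterion makes it Grade 3. On QTcF it is Grade 3 whatever the baseline.

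**Limit on heart rate alone.** At constant QTcF, reaching +60 ms on QTcB from 60 bpm needs HR = 60 × ((QTcF + 60)/QTcF)^6. At QTcF 420 ms this is about 134 bpm (139 bpm at 400 ms, 129 bpm at 440 ms). Heart rate alone is therefore unlikely to create a Grade 3 through the change criterion; its effect is mainly on the absolute bands.

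**The case against.** The strongest case on the other side is that this is a wording inconsistency with little consequence. QT and RR are both recorded, so QTcB can be derived and no information is lost. The action pathway in Section 4.5.5 runs on QTcF, and neither the discontinuation criteria in Section 4.6.1 nor Table 3 contains a QTc grade. ECG is not among the listed safety endpoints. Under Section 5.2.1, a deterioration in a clinical test such as an ECG counts as an adverse event when it brings symptoms or changes treatment, so most rate-driven shifts would never be reported as events. Section 6.5 plans displays, not a test of graded QTc, and details are left to a DAP that is not part of these documents. All of this stands and limits the seriousness of the point. It does not remove the contradiction, because the table is the stated scale and no text says which QTc it is applied to.

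Three stronger readings are tempting, and the documents do not support them:

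- **That the comparison with placebo is distorted.** At constant QTcF 430 ms, a fall from 95 to 75 bpm would move QTcB from 464 to 446 ms, from Grade 1 to ungraded. If heart rate changed differently by arm, grades would follow. But no heart-rate change, overall or by arm, is given, so this is a mechanism and not a shown effect.
- **That eligible patients enter with a Grade 3 adverse event.** A woman at QTcF 470 ms and 90 bpm has QTcB 470 × 1.070 = 503 ms, which falls in the Grade 3 band. However, Section 5.3.1 limits pre-dose reporting to serious events caused by a protocol-mandated intervention, and Section 5.3.5.9 sends pre-existing conditions to medical history unless they worsen. Such a grade could appear only in an ECG display. Part of the overlap would also remain on QTcF: women at 450 to 470 ms are Grade 1, and patients with wide QRS above 470 and up to 480 ms are Grade 2.
- **That a reading above the 500 ms trigger is always downgraded at slow heart rates.** The 505 ms example shows that this depends on baseline. At an unchanged 50 bpm, every baseline QTcF up to about 443 ms (430/0.970) still yields Grade 3. Section 4.5.5 also attaches no grade to its trigger.

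**Conclusion.** The inconsistency is real. Appendix 7 grades QTc on one correction, while Sections 4.1.2 and 4.5.5 screen, record and monitor on another, and nothing reconciles them. For readings near a cut-point and away from 60 bpm, heart rate alone can create or hide a QTc grade. For a given QTcF, the two values differ by −3% at 50 bpm, +5% at 80 bpm and +9% at 100 bpm.

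The conclusion rests on the definitions of the two corrections and on assumed heart rates. The number of patients affected cannot be computed. The effect is confined to QTc grades in ECG displays and in any QTc adverse event; it does not reach the efficacy analysis or any listed treatment rule. It should be corrected before the primary analysis because the correction costs almost nothing. The argument concerns consistency between measurement and grading; it does not say which correction is clinically preferable.

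**What to change.** Reconcile Sections 4.1.2, 4.5.5 and 6.5 with Appendix 7 so that QTc is graded on the quantity the trial records and monitors:

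1. In Appendix 7, make the QTc row refer to QTcF, using the modification allowance already stated in Section 5.3.3 and Appendix 7.
2. In Section 6.5 or the DAP, state that ECG grades are derived from the recorded QTcF. Show post-baseline grades against the baseline grade, because some eligible patients will still carry a grade at entry.
3. In the same edit, note that the trigger uses more than 60 ms and the Grade 3 criterion at least 60 ms, and say whether the difference is intended.

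The cost is one line in Appendix 7 and a sentence or two in Section 6.5 or the DAP, with no new data. The downside is that QTc grades will no longer match studies using the unmodified table, and that bands labelled for Bazett will be read on QTcF. A supplementary listing of QTcB-based grades, derived from the recorded QT and RR, would cover both.
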